7.1 Study Subjects

7.1.1 Disposition of Subjects

Subject disposition will be summarized with frequency tables.

7.1.2 Clinical Investigation Plan (CIP) Deviations

A study deviation is defined as an event when the investigator or site personnel did not conduct the study according to the protocol or the clinical trial agreement.

Study deviations must be reported, regardless of whether medically justifiable, pre-approved by the study leader, or taken to protect the subject in an emergency.

7.1.3 Analysis Sets

Full Analysis Set (FAS): All randomized subjects will be included in the analysis. For those subjects who do not complete a follow-up call, the analysis will include all data up to the last collected point or follow-up call. Subjects who completed the procedure phase will not be replaced. If the subject discontinues prior to randomization or during the procedure phase, she/he will be replaced, but will count toward the total sample size if they were randomized.

7.2 General Methodology

All statistical analyses will be performed using Statistical Analysis System (SAS) for Windows (version 9.3 or higher, SAS Institute Inc. Cary, NC) or other widely accepted statistical or graphical software. In general, data for all study subjects will be presented. Individual data will be presented in subject listings.

Descriptive statistics will be used to present the data and to summarize study outcomes. Discrete variables will be presented using frequency distributions and cross tabulations. Continuous variables will be summarized by presenting the number of observations (N), mean, standard deviation, median, minimum, and maximum values.

For safety assessments, adverse events will be summarized using frequency counts and percentages. Any unexpected adverse events will be reported and discussed.

7.2.1 BIS™ Value Analysis

Study subjects will be sequentially assigned to one of the target groups of anesthetics regimens while having BIS™ VISTA Monitoring System, the 4 Channel BISx, and BIS™ bilateral sensor placed on their forehead during these regimens to study the effects of these drugs on the brain. Each subject will be given a dose range of sequences of the target drug to achieve targeted drug concentration.

The modified Observer's Assessment of Alertness/Sedation (MOAA/S) scale will be used to perform sedation/ loss of consciousness assessment. Any subject who responds to any verbal command with MOAA/S assessment score of 2, 3, 4, and 5 will be considered as responsive. Subjects with MOAA/S assessment score of 0 and 1 will be considered unresponsive. Tetanic Electrical Stimulation (TES) will be employed with an MOAA/S assessment score of ≤ 2 for the first two subjects in each group and < 2 for all other subjects.

The BIS™ is a variable derived from the electroencephalograph (EEG) that has been reported to have the ability to measure the hypnotic component of the anesthetic state. It is a dimensionless number from 0 to 100, and decreasing values indicate more sedation and hypnosis.

The BIS™ index value collected from the left side of the brain will be used for primary analysis to reflect the typical operation of the device from this study. The BIS™ index value collected from the right side of the brain will be used for internal research purposes.

The logistic model (simplified Sigmoid E_{max} model) will be used to analyze the relationship between the BIS™ index and loss of responsiveness through the probability of response curves. The values of BIS™ at which 50% (BIS_{50}) and 95% (BIS_{95}) of subjects are unresponsive, and their 95% confidential intervals will be derived. The systematic variance between groups will be evaluated.

The logistic model is as follows:

$$P = \frac{e^{a+bX}}{1 + e^{a+bX}}$$

where P is the probability of “unresponsive”, X is the explanatory variable (BIS™ value or anesthetic agent concentration on the log scale), and a & b are model parameters.

For each regimen group, one can estimate the BIS™ value and the effect-site concentration at which 50% subjects are unresponsive, i.e., BIS₅₀ and EC₅₀ respectively. The corresponding 95% confidence intervals and standard errors for the estimates will be derived. The same evaluation will be performed for BIS₉₅, at which 95% subjects are unresponsive. The systematic variance between groups will be evaluated accordingly.

In addition, the Prediction Probability score (P_k) for correctly predicting if the subject was responsive or unresponsive will be estimated and reported (See details in reference: Smith 1996).

The interim review will be performed at the end of stage 1 when all subjects (50 subjects, 10 subjects in each regimen group) have completed the evaluation. BIS™ values will be estimated using the logistic model (Hill equation). One or more groups may be dropped upon interim results for safety concern (unacceptable safety events per clinical judgment). The pre-specific precision for BIS™ value estimation is $\pm 15\%$. For the final analysis, data from stage 1 and stage 2 will be combined by further taking to account poolability across sites (see details in the next section) and the adaptive nature of the 2-stage design (see details in the Appendix).

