7.3 Center Pooling

This is a multi-center clinical study, with standardization of subject enrollment, data entry and Adverse Event reporting. All investigational sites will follow the requirements of a common protocol, data collection procedures and forms. Upon justifications, data from all sites will be pooled for analysis.

Analyses to justify pooling will include the following:

Data Pooling Across Sites

Poolability across sites will be assessed using logistic regression model on the primary outcome. The model will include “Responsive: Yes/No” as response variable, and BIS, Site, BIS*Site interaction as exploratory variables. Sites with fewer than five subjects will be combined based on the order from smallest to largest. A P-value of 0.15 or less is considered statistically significant for the evaluation (FDA preferred).

If the sites are found to be significantly heterogeneous with respect to the primary outcome, additional analyses will be conducted to assess differences between sites in baseline and procedural variables that might explain differences in the primary outcome.

Data Pooling of Stage 1 and Stage 2

The study consists of two stages: first 10 subjects (stage 1), and then followed by 20 additional subjects (stage 2). Although no differences will be expected across the two stages, statistical testing will be performed to ensure the 2-stage data can be pooled for analysis. The testing will be based on the logistic regression model with binary “Responsive: Yes/No” as response variable, BIS, Stage indicator (X), BIS*X interaction as exploratory variables.

In case significant differences are present across the two stages, simply pooling data may not be valid. In this case, an alternative strategy will be used for statistical evaluation. Stage 1 data will be utilized as prior, which will be integrated into stage 2 data using the Bayesian Data Integration. More specifically, power prior and discounting function will be used to accommodate the difference across the two stages. Technical details can be found in the Appendix.

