7.7 Interim Review

The interim review will be performed at the end of stage 1 when all subjects have completed the evaluation. BIS™ values will be estimated using logistic regression (Hill equation) based on primary outcome “Responsive: Yes/No”. One or more regimens may be dropped upon interim results for safety concern (unacceptable safety events per clinical judgment).

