7.8 Evaluation of Objectives

The objective of this study is to investigate the relationship between BIS™ and anesthetic agents across a wide range of hypnotic states and to provide evidence to support BIS™ performance in use with these anesthetic agents.

Primary Objective:

To determine BIS₅₀ (BIS™ value at which 50% of subjects will be unresponsive at given drug concentrations).

Secondary Objective:

To determine BIS₉₅ (BIS™ value at which 95% of subjects will be unresponsive at given drug concentrations).

The logistic model (simplified Emax model) will be used to estimate the BIS™ values, along with corresponding 95% confidence intervals and standard errors.

Prediction Probability score (P_k) will be calculated following the details in the Smith's paper (Smith 1996). All technical details were provided in the Appendix in the paper. SAS procedure PROC LOGISTIC will be used to perform the calculation.

Differences in subject characteristics will be analyzed using t-test (continuous variables including age, weight and height) or Chi-square test (categorical variables including gender). The correlation coefficient for the relationship between sedation score and BIS™ value will be calculated for each group using a linear regression model. Additionally, BIS™ values and haemodynamic variables will be analyzed within the groups using analysis of variance (ANOVA) for repeated measures.

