From the above formula, we see that α_0 weights the historical data relative to the likelihood of the current data, and thus the parameter α_0 controls the influence of the historical data on $L(\theta|D)$. The parameter α_0 can be interpreted as a precision parameter for the historical data. Since D_0 is historical data, it is unnatural in practical applications to weight the historical data more than the current data; thus it is scientifically sound to restrict the range of α_0 to be between 0 and 1, that is, $0 \leq \alpha_0 \leq 1$. Setting $\alpha_0 = 1$ corresponds to the update of $\pi_0(\theta)$ using the Bayes theorem. That is, with $\alpha_0 = 1$ corresponds to the posterior distribution of θ based on the historical data D_0 . When $\alpha_0 = 0$, the prior does not depend on the historical data; in this case, $\pi(\theta|D_0, \alpha_0 = 0) = \pi_0(\theta)$. Thus, $\alpha_0 = 0$ is equivalent to a prior specification without incorporation of historical data. Therefore, the approach can be viewed as a generalization of the usual Bayesian update of $\pi_0(\theta)$. The parameter α_0 allows to control the influence of the historical data on the current study. Such control is important in cases where there is heterogeneity between the previous and current studies.

Since the power prior is essentially a likelihood function raised to a power, it shares all the properties that likelihood functions have, and therefore has several advantages over other non-likelihood-based priors. Due to its validity and ease of interpretation, the power prior approach has been widely adopted in practical applications and is commonly seen in medical device regulatory submissions.

[BIS] Statistical Analysis Plan

Revision [\[x\]](#)

Page 15 of 20

Form

Medtronic

B. Primary Efficacy Endpoint

In this study, the primary efficacy endpoint is the BIS₅₀, defined as the BIS™ value at which 50% of subjects are unresponsive at given drug concentrations. The BIS™ is a variable derived from the electroencephalograph (EEG) that has been reported to have the ability to measure the hypnotic component of the anesthetic state. It is a dimensionless number from 0 to 100, and decreasing values indicate more sedation and hypnosis. The MOAA/S scales and BIS™ value will be assessed and recorded when the subject is awake and at different drug concentrations.

The dose-response relationship will be estimated using the logistic model. The model is written as follows:

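### No subject-level variance is named for the BIS50, BIS95 and EC50 intervals or the pooling tests, although each subject gives several MOAA/S-BIS pairs; if thresholds differ materially between subjects, the fit described is over-precise

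*SAP*

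**What the plan says.** **Data.** Protocol 10.5 has MOAA/S and BIS taken awake and at each concentration step. SAP Appendix I, part B agrees: "The MOAA/S scales and BIS™ value will be assessed and recorded when the subject is awake and at different drug concentrations".

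**Primary model.** SAP 7.2.1 gives one logistic curve per regimen for the probability of being unresponsive. It has an intercept and a slope, and "X is the explanatory variable (BIS™ value or anesthetic agent concentration on the log scale), and a & b are model parameters". It then promises intervals for BIS50 and EC50, and the same evaluation for BIS95: "The corresponding 95% confidence intervals and standard errors for the estimates will be derived". No variance method is named.

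**Pooling tests.** SAP 7.3 uses logistic regression for both. The site model has "BIS, Site, BIS*Site interaction as exploratory variables" and is judged at p of 0.15 or less. The stage model has "BIS, Stage indicator (X), BIS*X interaction as exploratory variables", with no threshold stated. Neither has a subject term, and the SAP does not say which term or terms are tested.

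**Method names.** SAP 7.7 says "BIS™ values will be estimated using logistic regression (Hill equation) based on primary outcome". SAP 7.8 says "SAS procedure PROC LOGISTIC will be used to perform the calculation", but that sentence belongs to the Pk paragraph. The one repeated-measures method in 7.8 is for other outcomes: BIS and "haemodynamic variables will be analyzed within the groups using analysis of variance (ANOVA) for repeated measures".

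**Power prior.** The Compare model in Appendix I, part D has a normal error term indexed by i, where i is described as the subject. The power-prior likelihood does not say whether its unit is a subject or a single pair.

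**The concern.** Readings from one volunteer share that volunteer's sensitivity. Someone who stops responding at a high BIS will tend to look unresponsive at several successive readings. An ordinary logistic fit counts each reading as new information, while SAP Section 6 sizes the trial on subjects, one value each with a 25% CV.

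BIS50 with its 95% interval is the primary result, so reported precision is at stake. So is the analysis route: a significant stage difference under SAP 7.3 moves the final analysis from simple pooling to the power prior, where the unit is again unstated. A significant site difference only leads to further explanatory analyses.

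**Working it through.** **1. Pairs per subject (Protocol 10.5, listed steps plus the awake reading).** Sevoflurane regimens 8 + 1 = 9; desflurane 6 + 1 = 7; isoflurane 5 + 1 = 6. Stopping on BIS can shorten this; steps above those listed, or scoring during descent, can lengthen it. Thirty subjects therefore give up to 180 to 270 ascending pairs per regimen.

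**2. The plan's own figure (SAP 6).** Standardised difference 0.15/0.25 = 0.6, two-sided 0.05, power 80%. The one-sample t-test gives n = 24 (power 80.4%), so the stated 24 reproduces. The unit in that calculation is the subject.

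**3. A floor on precision.** Read the 25% CV as the between-subject SD of threshold at the SAP's simulation mean of 60: SD = 0.25 × 60 = 15 points. With 30 subjects the mean threshold cannot be known better than 15/√30 = 2.74 points (4.6%). The t half-width is 2.045 × 2.74 = 5.6 points, or 9.3% of 60.

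**4. Simulation of the ordinary fit (30 subjects, ascending pairs only).** Assumed, not in the documents: normal thresholds with mean 60, and BIS falling from 95 to 35.
- Set A: 6 or 9 pairs, within-subject logistic scale 4 or 8, reading noise SD 5, 1200-1500 runs.
- Set B: 5, 6 or 8 steps, scale 3, subject and reading SD 4 each, stopping after the first BIS below 40, 1000 runs.

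| Threshold SD | BIS50 coverage, set A | BIS50 coverage, set B |
|---|---|---|
| 0 | 94-95% | 94-96% |
| 1.25 | not run | 92-95% |
| 3 | 93-94% | not run |
| 5 | not run | 87-91% |
| 6 | 86-90% | not run |
| 10 | 75-88% | 75-84% |
| 15 | 70-82% | 71-78% |

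A further set gave 90-91% at SD 5, 79-85% at 10 and 67-80% at 15. Another gave 91-93% at SD 3, against 93-95% with no spread. BIS95 suffers less: 84-91% (A) and 82-87% (B) at SD 15.

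**5. Why coverage falls.** In set A at SD 15 the ordinary SE is 1.6-2.3 points, below the floor of 2.74; the true SD of the estimate is 3.0-3.4. The intervals have 1.6/3.0 = 0.53 to 2.3/3.4 = 0.68 of the proper width. Coverage ≈ 2Φ(1.96 × SE/SD) − 1, which gives about 70% at 0.53 and 82% at 0.68, as simulated.

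**6. Pooling tests with no true difference.** Likelihood-ratio tests, stage 10 against 20 subjects, with 0.15 assumed as the stage threshold.
- Joint test: 15-17% (A) or 18-23% (B) with no spread; 32-47% or 38-49% at SD 15.
- Stage main effect (A): 15-16% with no spread; 35-44% at SD 15.
- Interaction alone (A): 14-19% with no spread; 15-20% at SD 10; 17-27% at SD 15.
- Site joint test at its stated 0.15, three sites (B): 23-28% with no spread; 46-63% at SD 15.

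**7. With the subject as unit.** Subject-clustered SEs with t quantiles give BIS50 coverage of 94-97% at every spread in set A, and 93-96% in the further set.

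**The case against.** Several points on the other side stand.

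- **Silence is not an error.** A reader might infer that the SAP declares the pairs independent and is wrong as written. It does not. The formula fixes only the mean curve, PROC LOGISTIC is named only for Pk, SAP 7.2 allows other software, and Section 6 and the Appendix I, part F table count subjects. The charge is an unspecified variance, with an ordinary fit the natural reading.
- **Not every spread matters.** A reader might infer that any difference between subjects invalidates the intervals. At about 3 points or less the effect is negligible.
- **SD 15 is a reading of a planning CV.** The documents give no observed threshold SD.
- **Part of the pooling-test excess is not clustering.** The joint test already rejects 15-23% with no spread, partly from small-sample likelihood-ratio behaviour. The 0.15 is stated for sites only, and an interaction-only test is much less inflated.
- **The assumed BIS path is simple.** Desflurane and isoflurane subjects receive propofol before the first step, so their path is not a straight fall from awake. Uneven paths that were tried gave 80-82% coverage at SD 15: smaller, but still a shortfall.
- **No decision depends on interval width.** Groups are dropped only for safety, and between-group p-values are for reference. A reader might infer that the trial is too small. It is not shown to be: the corrected interval still meets ±15%.

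The error term in the Compare model is the nearest thing to a subject-level term. It serves only the weight given to stage 1 and supplies no variance for the intervals or the 7.3 tests.

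**Conclusion.** The concern holds in a conditional form. The SAP leaves the variance unspecified for its primary and secondary intervals and for both pooling tests. The fit it describes is over-precise if subjects differ materially in threshold.

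For 30 subjects and ascending pairs only, BIS50 coverage is about 87-91% at a threshold SD of 5, 75-88% at 10 and 67-82% at 15. BIS95 is affected less. At SD 15 the joint stage test at an assumed 0.15 rejects about 32-49% under no difference, against 15-23% with no spread. These sizes rest on the assumed spread, BIS path and within-subject scale; the direction does not.

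Priority: should be fixed before analysis. The harm is to reported precision and to the choice between pooling and the power prior, not to a pass/fail rule. The SD of 1.25 in the Appendix I, part F table, against 25% of 60 = 15, is a separate point to reconcile.

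**What to change.** 1. State which pairs enter the analysis: awake, ascending, descending. For desflurane and isoflurane, state how pairs taken after the propofol bolus are handled. The choice matters: in set B at SD 15, descending pairs that stop at return of response moved the fitted BIS50 from 60 to about 62-63.
2. Keep the marginal logistic curve. For the BIS50, BIS95 and EC50 intervals use subject-clustered variance with a small-sample correction and t quantiles, or a subject-level bootstrap.
3. Use a subject-clustered or subject-permutation test for site and stage. State the term or terms tested and the stage threshold. At SD 15 a clustered score test for stage rejected 15-21% at 0.15, and permutation 13-16% (150 trials only).
4. State that the subject is the unit in the Compare step and in the power-prior likelihood. A subject-specific random threshold is one way to do this; the choice is the sponsor's.

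**Cost.** SAP wording and modest programming, more for the power prior; no extra subjects or data. At SD 15 the reported BIS50 half-width grows from about 5-6% to about 10%. Over the full range of set A it goes from 1.96 × 1.6/60 = 5.2% to 1.96 × 2.3/60 = 7.5% with the ordinary fit, and from 2.045 × 3.0/60 = 10.2% to 2.045 × 3.4/60 = 11.6% when corrected. All are within ±15%. Clustered BIS95 intervals still under-cover slightly (92-95% at n = 30, about 90-92% at n = 10), and the report should say so.

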7.3 Center Pooling

This is a multi-center clinical study, with standardization of subject enrollment, data entry and Adverse Event reporting. All investigational sites will follow the requirements of a common protocol, data collection procedures and forms. Upon justifications, data from all sites will be pooled for analysis.

Analyses to justify pooling will include the following:

Data Pooling Across Sites

Poolability across sites will be assessed using logistic regression model on the primary outcome. The model will include “Responsive: Yes/No” as response variable, and BIS, Site, BIS*Site interaction as exploratory variables. Sites with fewer than five subjects will be combined based on the order from smallest to largest. A P-value of 0.15 or less is considered statistically significant for the evaluation (FDA preferred).

If the sites are found to be significantly heterogeneous with respect to the primary outcome, additional analyses will be conducted to assess differences between sites in baseline and procedural variables that might explain differences in the primary outcome.

Data Pooling of Stage 1 and Stage 2

The study consists of two stages: first 10 subjects (stage 1), and then followed by 20 additional subjects (stage 2). Although no differences will be expected across the two stages, statistical testing will be performed to ensure the 2-stage data can be pooled for analysis. The testing will be based on the logistic regression model with binary “Responsive: Yes/No” as response variable, BIS, Stage indicator (X), BIS*X interaction as exploratory variables.

In case significant differences are present across the two stages, simply pooling data may not be valid. In this case, an alternative strategy will be used for statistical evaluation. Stage 1 data will be utilized as prior, which will be integrated into stage 2 data using the Bayesian Data Integration. More specifically, power prior and discounting function will be used to accommodate the difference across the two stages. Technical details can be found in the Appendix.

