In terms of hypothesis testing, let BIS_{50} be unit 1. With 25% coefficient of variation, the standard deviation (σ) is calculated as $BIS_{50} \times CV = 0.25$. To detect 15% difference (allowable error), the target hypothesis can be written as:

$$H_0: \mu = 1 \quad vs. \quad H_a: \mu = 1.15.$$

With two-sided alpha of 0.05 and power of 80%, the required sample size is 24 (PASS – Tests for One Mean). Of note that the statistical approach has been published in the literature (see reference: Kopman 2011).

By further considering the interim review and adaptiveness of design, we expect at least 80% data information will be retained from Stage 1, leading to a minimum *effective sample size* of $10*0.8+20 = 28$ for the final analysis. Adding 2 more subjects to have 30 subjects in each regimen will ensure adequate data to evaluate the dose-response relationship.

7 Statistical Methods

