$$P = \frac{e^{a+bX}}{1 + e^{a+bX}}$$

where P is the probability of “unresponsive”, X is the explanatory variable (BIS™ value or anesthetic agent concentration on the log scale), and a & b are corresponding model parameters.

In the context of the dose-response model, let θ represents the target BIS™ value on the log scale. Let $D = \{y_1\}$ and $D_0 = \{y_0\}$ represent the current data and prior data respectively. The parameter estimation will be carried out based on the posterior distribution (upon normalization):

$$\pi(\theta|D, D_0, \widehat{\alpha}_0) \propto L(\theta|D) L(\theta|D_0)^{\widehat{\alpha}_0} \pi_0(\theta)$$

where the notation $\widehat{\alpha}_0$ is used to denote that the estimate of α_0 based on the observed data. Of note that the estimate depends on the current data (D) and prior data (D_0). In conjunction with a pre-specified decision rule controlling the prior data weight, the estimate of $\widehat{\alpha}_0$ represents a measure of similarity between the current data and prior data. Alternatively, in the absence of $\widehat{\alpha}_0$, i.e., full weight would be given to the prior data.

C. Statistical Analysis

The Bayesian power prior with discounting function will be used to estimate the target parameter and determine $\widehat{\alpha}_0$, the strength of the prior data used to support the current data. Of note $\widehat{\alpha}_0$ ranges from 0 to 1, where 1 means that 100% of the prior data is used and 0 means that no prior data is used. Before beginning the current study, an initial value is chosen for $\widehat{\alpha}_0$, and let's call this value α_{max} . This α_{max} value is the maximum strength that the prior data can receive. For this study, we intend to use the same protocol and enrollment criteria for the prior and current studies, and therefore believe that a value of $\alpha_{max} = 1$ is appropriate.

The study data will be analyzed using the power prior method along with discounting function. The method will discount α_{max} to an appropriate value $\widehat{\alpha}_0$ where $\widehat{\alpha}_0 \leq \alpha_{max}$. This discounting scale is based on the discounting function which will be discussed in detail in the next section.

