Under the adaptive procedure, if the current study data diverges from the prior data, the discounting function will discount the strength of the prior data. Alternatively, if the prior and current study data agree, there will be no or minimal penalty from the discounting function, thus a large amount of data information would be integrated into current data for statistical inferences.

The primary analysis set consists of all evaluable subjects and will be used for the primary analysis. The per-protocol set will be used for supportive analysis.

D. Discounting Function Estimation Method

The method of power prior discounting function is comprised of four steps: **Compare, Discount, Combine, and Estimate**. Details in each step are presented below.

Compare:

We start by stochastically comparing current data vs prior data as follows.

For each study group, we separately fit the model to the combined prior and current data:

$$H(p_i) = \beta_0 + \beta_1 I(i \in \text{prior}) + \beta_2 d_i + \varepsilon_i, \quad \varepsilon_i \sim N(0, \sigma^2),$$

where H is the inverse logit function, p_i is the probability of target response, d_i is the dose concentration (log scale), and the indication function $I(i \in \text{prior}) = 1$ if the subject is from the prior data, and 0 otherwise. With a flat prior on each parameter, we estimate the posterior probability that $\beta_1 > 0$ by first computing the parameter, using Monte Carlo sampling

$$p^* = P[\beta_1 > 0 \mid D, D_0].$$

Having calculated the parameter for each group, we use the transformation:

$$p = \begin{cases} 2p^*, & p^* \leq 0.5 \\ 2(1 - p^*), & p^* > 0.5 \end{cases}$$

Now, under this transformation, if p is close to 0, there is a high probability that the current data and prior data come from different populations and discounting should be applied to reduce the influence of the prior. On the other hand, if p is close to 1, there is a high probability that the current data and prior data are from similar populations and minimal discounting should be applied.

Discount:

[figure not shown]
Let discount α_{max} based on the value of p from the **Compare** step and the discounting function $F(p)$,

$$\widehat{\alpha_0} = \alpha_{max} F(p),$$

where $F(p)$ is a function between 0 and 1. A two-sided Weibull function will be utilized as follows:

$$F(p) = 1 - e^{-(p/\lambda)^k}.$$

For this study, we will be using a shape parameter of $k = 3$ and a scale parameter of $\lambda = 0.5$ (illustrated below).

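### SAP 7.3 runs the power prior only after a significant stage test, contrary to the rest of the plan, so chance can switch a regimen's primary BIS50 to an estimate that may lose most of Stage 1

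*SAP*

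**What the plan says.** SAP 7.3 (Data Pooling of Stage 1 and Stage 2) fits a logistic model for responsiveness with "BIS, Stage indicator (X), BIS*X interaction as exploratory variables". It does not say which term is tested or at what level; the 0.15 level in the same section is given for sites. It then says: "In case significant differences are present across the two stages, simply pooling data may not be valid". Only in that case does Stage 1 become a prior: "More specifically, power prior and discounting function will be used to accommodate the difference across the two stages". The same section introduces the test with "Although no differences will be expected across the two stages".

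Other places state no such condition. Appendix I.C says "The study data will be analyzed using the power prior method along with discounting function" and sets the maximum prior weight at 1. SAP 7.2.1 and Protocol 14.4 describe a final analysis that combines the stages with allowance for the two-stage design. The protocol names Bayesian integration as an example and leaves the details to the SAP.

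Appendix I.D turns a Compare probability p into the Stage 1 weight and explains that "if p is close to 0, there is a high probability that the current data and prior data come from different populations", in which case the prior should be discounted. SAP 6 nevertheless plans on substantial borrowing: "we expect at least 80% data information will be retained from Stage 1". The only interim action stated (SAP 7.7, Protocol 14.4) is dropping a regimen for safety.

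**The concern.** A discounting power prior is most useful at intermediate agreement, where it borrows part of the earlier data. SAP 7.3 pools at full weight whenever the test is not significant. It calls the power prior only after the test has declared a difference, where the discount function is built to return little.

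On the SAP's own expectation of no stage difference, a significant test is a chance finding. The regimen's primary BIS50 would then lean on the 20 Stage 2 subjects because they happened to differ from the first 10. That pulls the estimate away from the truth, and the interval takes no account of the selection. Because the sections disagree on when the method applies, and no trigger level is given, two analysts could follow the plan and report different primary results.

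**Working it through.** **Inputs.** From the SAP: 10 and 20 subjects per regimen (7.3); SD 0.25 and difference 0.15 with BIS50 set to 1, two-sided 0.05, 80% power (6); k = 3, λ = 0.5, maximum weight 1 (Appendix I.C and I.D). Assumed: a trigger level of 0.05 to 0.15, the upper end borrowed from the site test.

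1. *The plan's own figures.* A one-sample t-test (noncentral t) has power 0.785 at n = 23 and 0.804 at n = 24, so the required 24 is reproduced. The effective size is 10 × 0.8 + 20 = 28, also as stated. At n = 20 the same test has power 0.721.

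2. *Weight if Compare agrees with the trigger.* F(p) = 1 − exp(−(p/0.5)³).
   - F(0.05) = 1 − exp(−0.001) = 0.001
   - F(0.10) = 1 − exp(−0.008) = 0.008
   - F(0.15) = 1 − exp(−0.027) = 0.027
   - Effective n = 20 + 10F, so at most 20.01 (p ≤ 0.05) to 20.27 (p ≤ 0.15).
   - F reaches 0.80 only at p = 0.5 × (ln 5)^(1/3) = 0.586.

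3. *Weight if it does not agree.* Compare fits a stage indicator adjusted for log concentration, with no BIS and no interaction. The 7.3 model has BIS, stage and their interaction. An illustrative logistic simulation (4,000 trials per scenario, six steps per subject, assumed concentration–BIS curves, no true stage difference, trigger level 0.05 and 0.15) gave:

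| Term tested in 7.3 | Mean Stage 1 weight after a trigger, no between-subject variation | Same, between-subject SD of 8 BIS units | Coverage after a trigger, no between-subject variation |
|---|---|---|---|
| Stage main effect | 0.13–0.23 | 0.09–0.18 | 74%–85% |
| Stage and interaction (2 df) | 0.29–0.34 | 0.19–0.26 | 83%–87% |
| Interaction only | 0.46–0.48 | 0.42–0.48 | 92%–93% |

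   Coverage for the SD-of-8 scenario is left out. That fit ignores between-subject variation, and it covers only 84% over all trials with the power prior always used, so the loss there is not specific to the trigger.

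4. *Coverage on the planning model.* Take two stage means with no true difference and known variance σ². The stage difference has variance σ²(1/10 + 1/20) = 0.15σ². Its correlation with the Stage 2 mean has size 0.05/√(0.05 × 0.15) = 0.577, so selecting a large difference selects Stage 2 means far from the truth. The pooled mean has zero covariance with the difference: (1/3)(σ²/10) − (2/3)(σ²/20) = 0. Four million draws gave coverage after a trigger of 76.9%, 82.1% and 85.0% at levels 0.05, 0.10 and 0.15. The pooled interval in those same trials covered 94.9% to 95.0%. Root mean squared error after a trigger was 1.94, 1.78 and 1.68 times that of pooling.

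5. *Whole procedure.* At level 0.05: 0.05 × 0.769 + 0.95 × 0.95 = 0.941. At level 0.15: 0.15 × 0.850 + 0.85 × 0.95 = 0.935.

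6. *Five regimens, assumed independent.* 1 − 0.95⁵ = 0.226; 1 − 0.85⁵ = 0.556.

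7. *If the stages truly differ by 15%.* The pooled mean lies 0.15 × 10/30 = 0.05 from the Stage 2 value. Its standard error is 0.25/√30 = 0.0456, so the shift is 1.095 standard errors. Coverage of the Stage 2 value is Φ(0.865) − Φ(−3.055) = 0.805, about 81%. After a trigger, the planned procedure covers the Stage 2 value about 92% to 95% of the time.

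**The case against.** The strongest reply has four parts.

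- **The trigger and the weight come from different models.** A reader might infer that a triggered analysis is always Stage 2 alone. The documents do not support that: the limits in step 2 hold only if the two p-values agree, and step 3 shows much larger weights when the interaction is the term tested. This stands, and the point is limited accordingly. It does not rescue the rule, because the weight is then only loosely tied to what triggered it.
- **The low coverage is conditional.** A reader might infer that the study's 95% intervals cover 77% to 85%. They do not: over all trials the loss is about 1 to 1.5 percentage points. The conditional figure still matters, because results are reported by regimen and a triggered regimen is identifiable.
- **A stage check has a use.** A reader might infer that the test is pointless because no BIS result alters Stage 2. That goes too far. SAP 7.2.1 and Protocol 14.3 give the first two subjects in each group a different rule for electrical stimulation, and the protocol's version history suggests that procedures changed. Looking for drift is reasonable; letting the test choose the primary estimator is the problem.
- **Pooling has its own cost.** With a true 15% difference it misses the Stage 2 value more often (step 7). This also stands, so the estimand has to be named.

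If the unconditional sections govern instead, the trigger never operates. But 7.3 is explicit, and nothing says which section prevails.

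**Conclusion.** The plan is wrong as written: it gives two incompatible rules for the primary estimate, and the explicit one lets a preliminary test change the estimator. Where Compare agrees with the trigger, a triggered regimen rests in effect on about 20 subjects. That means 72% power in the SAP's own test, against a required 24 and an expected effective size of at least 28. Elsewhere the weight kept averaged roughly 0.1 to 0.5 in the illustrative check, still well short of the 80% planned.

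The coverage figures (about 77% to 85% after a chance trigger, 93.5% to 94% overall) and the 23% to 56% chance of at least one trigger rest on no true stage difference, an assumed level of 0.05 to 0.15, the normal planning model with trigger and weight measuring the same contrast, and independent regimens. They do not apply if the stages truly differ. The logistic results rest on assumed curves and only illustrate how far the answer depends on the term tested.

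**What to change.** State one rule in SAP 7.3, 7.2.1 and Appendix I.C, and align Protocol 14.4:

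- Make full-weight pooling of both stages the primary analysis in every regimen, with no preliminary stage test.
- Name the estimand as the BIS50 over all enrolled subjects of the regimen, both stages together.
- Report the stage and BIS-by-stage terms descriptively.
- Report the power-prior and Stage 2-only estimates as sensitivity analyses in all five regimens, whatever those terms show.

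Using the power prior in every regimen would also remove the trigger. On the planning model with equal stages, however, it keeps a mean weight of 0.554 (effective n 20 + 10 × 0.554, about 25.5) and covers about 93.8%, so pooling is the better primary choice under the SAP's expectation of no stage difference.

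The cost is wording in the SAP and a matching edit to the protocol, which needs ethics approval under Protocol 16.6 if made as an amendment. The statistical price is that a real stage difference would appear in the sensitivity analyses and would not change the primary estimate. The change should be made before the two stages are compared.
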